7.1.4. Temporary Discontinuation

Temporary discontinuation from study intervention treatment is allowed secondary to hospitalization, personal or exceptional circumstances, or to evaluate the study intervention impact on an uncertain AE.

Study intervention may be restarted at the investigator's discretion.

If temporary discontinuation is due to an AE, it should be reported to the sponsor-designated medical monitor. Temporary treatment discontinuation and re-starting should be documented. Restarting treatment after a discontinuation period that is greater than 12 weeks should be discussed between the investigator and sponsor-designated medical monitor.

7.2. Participant Discontinuation/Withdrawal from the Study

A participant may withdraw from the study

- at any time at the participant's own request
- at the request of the participant's designee (for example, parents or legal guardian)
- at the discretion of the investigator for safety, behavioral, compliance, or administrative reasons
- if enrollment in any other clinical study involving an investigational product or enrollment in any other type of medical research judged not to be scientifically or medically compatible with this study, or
- if the participant, for any reason, requires treatment with another therapeutic agent that has been demonstrated to be effective for treatment of the study indication, discontinuation from the study occurs prior to introduction of the new agent.

Discontinuation is expected to be uncommon.

At the time of discontinuing from the study, if possible, an early discontinuation visit should be conducted, as shown in the SoA. See SoA for data to be collected at the time of study discontinuation and follow-up and for any further evaluations that need to be completed. The participant will be permanently discontinued from both the study intervention and the study at that time.

If the participant withdraws consent for disclosure of future information, the sponsor may retain and continue to use any data collected before such a withdrawal of consent. If a participant withdraws from the study, he/she may request destruction of any samples taken and not tested, and the investigator must document this in the site study records.

7.3. Lost to Follow up

A participant will be considered lost to follow-up if he or she repeatedly fails to return for scheduled visits and is unable to be contacted by the study site. Site personnel or designee are expected to make diligent attempts to contact participants who fail to return for a scheduled visit or were otherwise unable to be followed up by the site.

Site personnel, or an independent third party, will attempt to collect the vital status of the participant within legal and ethical boundaries for all participants randomized, including those who did not get investigational product. Public sources may be searched for vital status information. If vital status is determined to be deceased, this will be documented and the participant will not be considered lost to follow-up. Sponsor personnel will not be involved in any attempts to collect vital status information.

8. Study Assessments and Procedures

- Study procedures and their timing are summarized in the SoA.
- Immediate safety concerns should be discussed with the sponsor immediately upon occurrence or awareness to determine if the participant should continue or discontinue study intervention.
- Adherence to the study design requirements, including those specified in the SoA, is essential and required for study conduct.
- All screening evaluations must be completed and reviewed to confirm that potential participants meet all eligibility criteria. The investigator will maintain a screening log to record details of all participants screened and to confirm eligibility or record reasons for screening failure, as applicable.

8.1. Efficacy Assessments

8.1.1. Biomarker Efficacy Measures Florbetapir F18 PET scan

Change in amyloid burden (as assessed with florbetapir F18 PET by personnel blinded to treatment allocation) will be compared in donanemab and aducanumab-treated participants.

8.2. Safety Assessments

Planned time points for all safety assessments are provided in the SoA.

8.2.1. Vital Signs

For each participant, vital signs measurements should be conducted according to the SoA (Section 1.3) and following the study-specific recommendations included in Manual of Operations for the study.

8.2.2. Electrocardiograms

For each participant, single 12-lead digital ECGs will be collected during the screening period, according to the SoA (Section 1.3) using an ECG machine that automatically calculates the heart rate and measures PR, QRS, QT, and QTc intervals. Refer to Section 7.1.2 for QTc withdrawal criteria and any additional QTc readings that may be necessary. Participants must be supine for approximately 5 to 10 minutes before ECG collection and remain supine but awake during ECG collection.

Electrocardiograms may be obtained at additional times, when deemed clinically necessary.

Electrocardiograms will be interpreted by a qualified physician (the investigator or qualified designee) at the site as soon after the time of ECG collection as possible, and ideally while the participant is still present, to determine whether the participant meets entry criteria at the relevant visit(s) and for immediate participant management, should any clinically relevant findings be identified.

After enrollment, if a clinically significant increase in the QT/QTc interval from baseline or other clinically significant quantitative or qualitative change from baseline is identified, the participant will be assessed by the investigator for symptoms (e.g., palpitations, near syncope, syncope) and to determine whether the participant can continue in the study. The investigator or qualified designee is responsible for determining if any change in participant management is needed.

The investigator (or qualified designee) must document his/her review of the ECG printed at the time of collection and any alert reports.

8.2.3. Clinical Safety Laboratory Tests

- See Appendix 2 for the list of clinical laboratory tests to be performed and the SoA for the timing and frequency.
- The investigator must review the laboratory results, document this review, and report any clinically relevant changes occurring during the study as an AE. The laboratory results must be retained with source documents unless a Source Document Agreement or comparable document cites an electronic location that accommodates the expected retention duration. Clinically significant abnormal laboratory findings are those which are not associated with the underlying disease, unless judged by the investigator to be more severe than expected for the participant's condition.
- All laboratory tests with values considered clinically significantly abnormal during participation in the study or within the follow-up period after the last dose of study intervention after the last dose of study intervention should be repeated until the values return to normal or baseline or are no longer considered clinically significant by the investigator or medical monitor.
 - If such values do not return to normal/baseline within a period of time judged reasonable by the investigator, the etiology should be identified and the sponsor notified.
 - All protocol-required laboratory assessments, as defined in Appendix 2, must be conducted in accordance with the SoA, standard collection requirements, and laboratory manual.
- If laboratory values from non-protocol specified laboratory assessments performed at an investigator-designated local laboratory require a change in participant management or are considered clinically significant by the investigator (e.g., SAE or AE or dose modification), then report the information as an AE.

8.2.4. Suicidal Ideation and Behavior Risk Monitoring

Participants being treated with study intervention should be monitored appropriately and observed closely for SIB or any other unusual changes in behavior, especially at the beginning and end of the course of intervention, or at the time of dose changes, either increases or decreases. Participants who experience signs of SIB should undergo a risk assessment. All factors contributing to SIB should be evaluated and consideration should be given to discontinuation of the study intervention.

Baseline assessment of SIB and intervention-emergent SIB will be monitored during Study AACN using the C-SSRS.

C-SSRS

C-SSRS is a scale that captures the occurrence, severity, and frequency of SIB during the assessment period via a questionnaire. The scale was developed by the NIMH trial group for the purpose of being counterpart to the C-CASA categorization of suicidal events.

8.2.5. Magnetic Resonance Imaging

MRI of the brain will be performed according to the SoA (Section 1.3) and as clinically indicated. Unscheduled MRIs may be performed at the discretion of investigator.

This technology will be used to check for evidence of ARIA-H or ARIA-E, and other clinically relevant inclusion/exclusion and safety findings.

The MRI scans will be reviewed by the investigator or qualified designee for immediate participant management. Any clinically significant findings noted at baseline that result in a diagnosis should be recorded as a preexisting condition or AE. MRI scans are read locally and will be sent for analysis to a centralized MRI vendor (blinded to treatment allocation) designated by Lilly. Final MRI eligibility at screening will be determined by the centralized MRI vendor designated by Lilly and the MRI results will be reported to the investigator as “does” or “does not” meet MRI eligibility criteria.

Specific analyses of the scans, including assessments of ARIA-H and ARIA-E, will be interpreted by the centralized MRI vendor for data analysis and report-writing purposes.

Results of centrally read MRIs regarding participant care/safety will be reported back to the investigator.

8.2.6. Hepatic Safety Monitoring

Close hepatic monitoring

Laboratory tests (Appendix 6, Section 10.6), including ALT, AST, ALP, TBL, D. Bil, GGT, and CK, should be repeated within 48 to 72 hours to confirm the abnormality and to determine if it is increasing or decreasing, if one or more of these conditions occur:

If a participant with baseline results of ...	develops the following elevations:
ALT or AST <1.5x ULN	ALT or AST \geq 3x ULN
ALP <1.5x ULN	ALP \geq 2x ULN
TBL <1.5x ULN	TBL \geq 2x ULN (except for participants with Gilbert's syndrome)
ALT or AST \geq 1.5x ULN	ALT or AST \geq 2x baseline

ALP $\geq 1.5x$ ULN	ALP $\geq 2x$ baseline
TBL $\geq 1.5x$ ULN	TBL $\geq 1.5x$ baseline (except for participants with Gilbert's syndrome)

If the abnormality persists or worsens, clinical and laboratory monitoring, and evaluation for possible causes of abnormal liver tests should be initiated by the investigator in consultation with the Lilly-designated medical monitor. At a minimum, this evaluation should include physical examination and a thorough medical history, including symptoms, recent illnesses (for example, heart failure, systemic infection, hypotension, or seizures), recent travel, history of concomitant medications (including over-the-counter), herbal and dietary supplements, history of alcohol drinking and other substance abuse.

Initially, monitoring of symptoms and hepatic biochemical tests should be done at a frequency of 1 to 3 times weekly, based on the participant's clinical condition and hepatic biochemical tests. Subsequently, the frequency of monitoring may be lowered to once every 1 to 2 weeks, if the participant's clinical condition and lab results stabilize. Monitoring of ALT, AST, ALP, and TBL should continue until levels normalize or return to approximate baseline levels.

Comprehensive hepatic evaluation

A comprehensive evaluation should be performed to search for possible causes of liver injury if one or more of these conditions occur:

If a participant with baseline results of...	develops the following elevations:
ALT or AST $< 1.5x$ ULN	ALT or AST $\geq 3x$ ULN with hepatic signs/symptoms ^a , or ALT or AST $\geq 5x$ ULN
ALP $< 1.5x$ ULN	ALP $\geq 3x$ ULN
TBL $< 1.5x$ ULN	TBL $\geq 2x$ ULN (except for participants with Gilbert's syndrome)
ALT or AST $\geq 1.5x$ ULN	ALT or AST $\geq 2x$ baseline with hepatic signs/symptoms ^a , or ALT or AST $\geq 3x$ baseline
ALP $\geq 1.5x$ ULN	ALP $\geq 2x$ baseline
TBL $\geq 1.5x$ ULN	TBL $\geq 2x$ baseline (except for participants with Gilbert's syndrome)

^a Hepatic signs/symptoms are severe fatigue, nausea, vomiting, right upper quadrant abdominal pain, fever, rash, and/or eosinophilia $> 5\%$.

At a minimum, this evaluation should include physical examination and a thorough medical history, as outlined above, as well as tests for PT-INR; tests for viral hepatitis A, B, C, or E; tests for autoimmune hepatitis; and an abdominal imaging study (for example, ultrasound or CT scan).

Based on the participant's history and initial results, further testing should be considered in consultation with the Lilly-designated medical monitor, including tests for hepatitis D virus, cytomegalovirus, Epstein-Barr virus, acetaminophen levels, acetaminophen protein adducts, urine toxicology screen, Wilson's disease, blood alcohol levels, urinary ethyl glucuronide, and blood phosphatidylethanol. Based on the circumstances and the investigator's assessment of the participant's clinical condition, the investigator should consider referring the participant for a hepatologist or gastroenterologist consultation, magnetic resonance cholangiopancreatography, endoscopic retrograde cholangiopancreatography, cardiac echocardiogram, or a liver biopsy.

Additional hepatic data collection (hepatic safety CRF) in study participants who have abnormal liver tests during the study

Additional hepatic safety data collection in hepatic safety CRF should be performed in study participants who meet 1 or more of the following 5 conditions:

1. Elevation of serum ALT to $\geq 5x$ ULN on 2 or more consecutive blood tests (if baseline ALT $< 1.5x$ ULN)
 - In participants with baseline ALT $\geq 1.5x$ ULN, the threshold is ALT $\geq 3x$ baseline on 2 or more consecutive tests
2. Elevated TBL to $\geq 2x$ ULN (if baseline TBL $< 1.5x$ ULN) (except for cases of known Gilbert's syndrome)
 - In participants with baseline TBL $\geq 1.5x$ ULN, the threshold should be TBL $\geq 2x$ baseline
3. Elevation of serum ALP to $\geq 2x$ ULN on 2 or more consecutive blood tests (if baseline ALP $< 1.5x$ ULN)
 - In participants with baseline ALP $\geq 1.5x$ ULN, the threshold is ALP $\geq 2x$ baseline on 2 or more consecutive blood tests
4. Hepatic event considered to be a SAE
5. Discontinuation of study drug due to a hepatic event

Note: the interval between the two consecutive blood tests should be at least 2 days.

8.3. Adverse Events, Serious Adverse Events, and Product Complaints

The definitions of the following events can be found in Appendix 3:

- AEs
- SAEs
- PCs

These events will be reported by the participant (or, when appropriate, by a caregiver, surrogate, or the participant's legally authorized representative).

The investigator and any qualified designees are responsible for detecting, documenting, and recording events that meet these definitions and remain responsible for following up events that

are serious, considered related to the study intervention or study procedures, or that caused the participant to discontinue the study intervention or study (see Section 6.8.3).

Care will be taken not to introduce bias when detecting events. Open-ended and non-leading verbal questioning of the participant is the preferred method to inquire about event occurrences.

After the initial report, the investigator is required to proactively follow each participant at subsequent visits/contacts. All SAEs and AEs of special interest (as defined in Section 8.3.4) will be followed until resolution, stabilization, the event is otherwise explained, or the participant is lost to follow-up (as defined in Section 7.3). For PCs, the investigator is responsible for ensuring that follow-up includes any supplemental investigations as indicated to elucidate the nature and/or causality. Further information on follow-up procedures is provided in Appendix 10.3.

8.3.1. Timing and Mechanism for Collecting Events

This table describes the timing, deadlines, and mechanism for collecting events.

Event	Collection Start	Collection Stop	Timing for Reporting to Sponsor or Designee	Mechanism for Reporting	Back-Up Method of Reporting
Adverse Event					
AE	Signing of the ICF	Participation in study has ended	As soon as possible upon site awareness	AE CRF	N/A
Serious Adverse Event					
SAE and SAE updates – prior to start of study intervention and deemed reasonably possibly related with study procedures or occurring after receiving PET tracer	Signing of the ICF	Start of intervention	Within 24 hours of awareness	SAE CRF	SAE paper form
SAE and SAE updates – after start of study intervention	Start of intervention	Participation in study has ended	Within 24 hours of awareness	SAE CRF	SAE paper form

Event	Collection Start	Collection Stop	Timing for Reporting to Sponsor or Designee	Mechanism for Reporting	Back-Up Method of Reporting
SAE ^a – after participant’s study participation has ended and the investigator becomes aware	After participant’s study participation has ended	N/A	Promptly	SAE paper form	N/A
Pregnancy					
Pregnancy in female participants and female partners of male participants	After the start of study intervention	90 days after the last dose	Within 24 hours (see Section 8.3.2)	Pregnancy paper form	N/A
Product Complaints					
PC associated with an SAE or might have led to an SAE	Start of study intervention	End of study intervention	Within 24 hours of awareness	PC form	N/A
PC not associated with an SAE	Start of study intervention	End of study intervention	Within 1 business day of awareness	PC form	N/A
Updated PC information	—	—	As soon as possible upon site awareness	Originally completed PC form with all changes signed and dated by the investigator	N/A
PC (if investigator becomes aware)	Participation in study has ended	N/A	Promptly	PC form	

Abbreviations: AE = adverse event; CRF = case reporting form; ICF = informed consent form; N/A = not applicable; PC = product complaint; PET = positron emission tomography; SAE = serious adverse event.

^a SAEs after study participation should not be reported unless the investigator deems them to be possibly related to study treatment or study participation.

8.3.2. Pregnancy

Collection of pregnancy information

Male participants with partners who become pregnant

- a. The investigator will attempt to collect pregnancy information on any male participant's female partner who becomes pregnant while the male participant is in this study. This applies only to male participants who receive study intervention.
- b. After learning of a pregnancy in the female partner of a study participant, the investigator will
 - a. obtain a consent to release information from the pregnant female partner directly, and
 - b. within 24 hours after obtaining this consent will record pregnancy information on the appropriate form and submit it to the sponsor.

The female partner will also be followed to determine the outcome of the pregnancy. Information on the status of the mother and child will be forwarded to the sponsor. Generally, the follow-up will be no longer than 6 to 8 weeks following the estimated delivery date. Any termination of the pregnancy will be reported regardless of gestational age, fetal status (presence or absence of anomalies) or indication for the procedure.

Female participants who become pregnant

- a. The investigator will collect pregnancy information on any female participant who becomes pregnant while participating in this study. The initial information will be recorded on the appropriate form and submitted to the sponsor within 24 hours of learning of a participant's pregnancy.
- b. The participant will be followed to determine the outcome of the pregnancy. The investigator will collect follow-up information on the participant and the neonate and the information will be forwarded to the sponsor. Generally, follow-up will not be required for longer than 6 to 8 weeks beyond the estimated delivery date. Any termination of pregnancy will be reported, regardless of gestational age, fetal status (presence or absence of anomalies) or indication for the procedure.
- c. While pregnancy itself is not considered to be an AE or SAE, any pregnancy complication or elective termination of a pregnancy for medical reasons will be reported as an AE or SAE.
- d. A spontaneous abortion (occurring at <20 weeks gestational age) or still birth (occurring at ≥20 weeks gestational age) is always considered to be an SAE and will be reported as such.

- e. Any post-study pregnancy related SAE considered reasonably related to the study intervention by the investigator will be reported to the sponsor as described in protocol Section 8.3.1. While the investigator is not obligated to actively seek this information in former study participants, he or she may learn of an SAE through spontaneous reporting.
- f. Any female participant who becomes pregnant while participating in the study will discontinue study intervention. If the participant is discontinued from the study, follow the standard discontinuation process and continue directly to the follow-up phase. The follow-up on the pregnancy outcome should continue independent of intervention or study discontinuation.

8.3.3. Hypersensitivity Including Infusion-Related Reactions

8.3.3.1. Management of Infusion-Related Reactions

If a systemic hypersensitivity reaction occurs, additional data describing each sign or symptom should be provided to the sponsor in the Hypersensitivity, Anaphylactic, and Infusion-Related Reactions CRF. Participants who experience a systemic hypersensitivity, should have vital signs collected.

Locations where study participants are receiving study intervention should have appropriately trained medical staff and appropriate resuscitation equipment and rescue measures. It is recommended that participants who experience a systemic hypersensitivity reaction be treated per the local standard of care.

If a participant experiences a systemic hypersensitivity reaction or infusion-related reaction either involving 2 or more organ systems (for example, mucocutaneous, respiratory, cardiovascular, or gastrointestinal systems), or that is severe, additional blood and urine samples should be collected as close to the event as possible, as described in Section 10.2.1. Tryptase and when applicable urine *N*-methylhistamine should be repeated in approximately 4 weeks (and prior to the next infusion, if applicable) to obtain post-event baseline. Laboratory results are provided to the sponsor via the central laboratory and are not needed for clinical management of the participant.

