8.3.3.2. Dosing Rechallenge and Premedication for Infusions

Donanemab

Premedication for dosing is not planned. Dosing rechallenge is contraindicated in participants that have experienced a suspected or possible anaphylactic reaction (for example, reaction involving 2 or more organ systems [for example, mucocutaneous, respiratory, cardiovascular, or gastrointestinal systems] occurring in close proximity to dosing), in a prior dose (Sampson et al. 2006). For infusion-related reactions which are not suspicious for anaphylaxis, at the investigator's discretion, the participant may continue to receive study intervention. The participant may be premedicated for subsequent doses at investigator's discretion and according to local practice guidelines. Any premedication given will be documented as a concomitant therapy (Section 6.8).

Aducanumab

Investigators should consult the product label and follow local practice.

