- The investigator will attempt to establish a diagnosis of the event based on signs, symptoms, and/or other clinical information. Whenever possible, the diagnosis (not the individual signs/symptoms) will be documented as the AE/SAE.

Assessment of Intensity

The investigator will make an assessment of intensity for each AE and SAE reported during the study and assign it to one of the following categories:

- **Mild:** A type of adverse event that is usually transient and may require only minimal treatment or therapeutic intervention. The event does not generally interfere with usual activities of daily living.
- **Moderate:** A type of adverse event that is usually alleviated with additional specific therapeutic intervention. The event interferes with usual activities of daily living, causing discomfort but poses no significant or permanent risk of harm to the research participant.
- **Severe:** A type of AE that interrupts usual activities of daily living, or significantly affects clinical status, or may require intensive therapeutic intervention. An AE that is assessed as severe should not be confused with a SAE. Severe is a category utilized for rating the intensity of an event; and both AEs and SAEs can be assessed as severe.

An event is defined as 'serious' when it meets at least one of the predefined outcomes as described in the definition of an SAE, NOT when it is rated as severe.

Assessment of Causality

- The investigator is obligated to assess the relationship between study intervention and each occurrence of each AE/SAE. The investigator will use clinical judgment to determine the relationship

- A “reasonable possibility” of a relationship conveys that there are facts, evidence, and/or arguments to suggest a causal relationship, rather than a relationship cannot be ruled out.
- Alternative causes, such as underlying disease(s), concomitant therapy, and other risk factors, as well as the temporal relationship of the event to study intervention administration will be considered and investigated.
- The investigator will also consult the IB and/or Product Information, for marketed products, in their assessment.
- For each AE/SAE, the investigator **must** document in the medical notes that he/she has reviewed the AE/SAE and has provided an assessment of causality.

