4.7.2. Adverse Events

Treatment-emergent adverse events (TEAEs) will be defined as events that first occurred or worsened after the randomization date (Visit 2 date). Should there be insufficient data for AE start date, stop date, and time to make this comparison, the AE will be considered treatment-emergent. The MedDRA lower-level term (LLT) will be used in the treatment-emergent computation. The maximum severity for each lower-level term (LLT) during the baseline period will be used as baseline.

An overview of AEs, including the number and percentage of participants who died, suffered serious adverse events (SAEs), discontinued due to AEs and who suffered TEAEs, will be provided. Comparison between treatments will be performed using Fisher’s Exact Test.

Summaries of AEs by decreasing frequency of PT within SOC will be provided for the following:

- Preexisting conditions
- TEAEs
- TEAEs by maximum severity
- TEAEs occurring in greater than or equal to 2% of participants by PT
- Serious adverse events
- Adverse events reported as reason for study treatment discontinuation

These summaries will include number and percentages of participants with TEAEs. Treatment comparisons will be carried out using Fisher's Exact Test.

Hypersensitivity and Infusion-Related Reactions (IRR) will be summarized and compared between treatment groups using Fisher's Exact test. Hypersensitivity and IRR will be broken out between Potential Immediate (defined as TEAEs occurring on the date of infusions) and Potential Non-Immediate (defined as TEAEs not occurring on the date of infusions but prior to the administration of a subsequent infusion). The following will be used to identify such TEAEs:

- Anaphylactic reaction SMQ (20000021; narrow, algorithm per SMQ guide, and broad)
- Hypersensitivity SMQ (20000214; narrow and broad)
- Angioedema SMQ (20000024; narrow and broad)
- Event maps to Preferred Term (PT) of Infusion related reaction (10051792)

The number and percentage of participants who experienced a TEAE for the following will be analyzed:

- Any narrow or algorithmic term from any one of the 3 SMQs indicated above (that is, combined search across narrow and algorithmic portions of all 3 SMQs)
- Any narrow scope term within each SMQ, separately (that is, narrow SMQ search)
- Any term within each SMQ, separately (that is, broad SMQ search)

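### SAP 4.7.2 classifies hypersensitivity reactions from coded adverse-event terms alone and plans no output from the CRF that holds their signs and symptoms, so classification as possible anaphylaxis depends on the investigator's choice of term

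*Protocol*

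**What the plan says.** **Where signs and symptoms go.** Protocol 8.3.3.1 covers systemic hypersensitivity reactions: "additional data describing each sign or symptom should be provided to the sponsor in the Hypersensitivity, Anaphylactic, and Infusion-Related Reactions CRF". Protocol 6.8.2 names the same form for infusion reactions.

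**What goes on the adverse-event page.** Protocol Appendix 3, section 10.3.4: "Whenever possible, the diagnosis (not the individual signs/symptoms) will be documented as the AE/SAE".

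**How the SAP finds cases.** SAP 4.7.2 introduces its identifiers with "The following will be used to identify such TEAEs". There are three SMQs (anaphylactic reaction, hypersensitivity and angioedema) and one preferred term: "Event maps to Preferred Term (PT) of Infusion related reaction (10051792". The anaphylaxis entry is "Anaphylactic reaction SMQ (20000021; narrow, algorithm per SMQ guide, and broad". Hypersensitivity and IRRs are compared between arms with Fisher's exact test and split by whether they fall on an infusion day. The itemised counts are all of participants with a TEAE; the first is a "combined search across narrow and algorithmic portions of all 3 SMQs".

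**Multi-system wording.** Under the donanemab heading, Protocol 8.3.3.2 illustrates a suspected or possible anaphylactic reaction as "reaction involving 2 or more organ systems [for example, mucocutaneous, respiratory, cardiovascular, or gastrointestinal systems] occurring in close proximity to dosing". Section 8.3.3.1 uses a similar criterion, or severity, to trigger extra samples in either arm.

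**Status of the topic.** Protocol 8.3.4 makes hypersensitivity, including IRRs and anaphylaxis, a topic of special interest and leaves its analysis to the SAP.

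**The concern.** The information that shows how many organ systems a reaction involved sits on one form, and the planned search reads another. A site that follows 10.3.4 may enter a single diagnosis for a reaction with skin, respiratory and blood-pressure signs and describe those signs only on the hypersensitivity CRF. The SAP would then see only the diagnosis term.

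If the investigator writes anaphylaxis, the narrow search should find it. If the investigator writes infusion related reaction, the event enters the IRR summary, but nothing planned in the SAP checks whether it was multi-system.

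At stake is how an adverse event of special interest is described by arm, in a trial where the person choosing the term knows the treatment. The prompts also differ: 8.3.3.2 gives the organ-system description under donanemab, and for aducanumab it points to the product label and local practice. Different labelling by arm is therefore possible, though nothing shows that it will happen.

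**Working it through.** The documents give no rate, count or power for anaphylaxis, so there is no figure to reproduce. The check is mainly a comparison of texts.

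**1. Data capture against analysis**

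| Item | Adverse-event page | Hypersensitivity CRF |
|---|---|---|
| Diagnosis term | Yes, preferred (10.3.4) | Not stated |
| Each sign or symptom | Only if no diagnosis is given, or if the site adds them | Yes (8.3.3.1) |
| Read by the SAP 4.7.2 searches | Yes | No |
| Any planned SAP table, test or listing | Yes | None found |

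The SAP text contains no output from the hypersensitivity CRF, no organ-system count and no review of anaphylaxis against clinical criteria. By contrast, SAP 4.7.3 does plan a listing of the hepatic-safety CRF.

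**2. What follows.** The documents do not set out how the SMQ algorithm combines terms; the SAP only refers to the guide. The conclusion does not need those details. A search defined on coded TEAEs, whether narrow, algorithmic or broad, cannot use a sign or symptom that exists only on another form.

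**3. What does not follow.** A reaction entered under the preferred term Infusion related reaction is identified and falls within the IRR comparison. What can be lost is its classification as multi-system or possible anaphylaxis.

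**4. Illustration of size.** Inputs:
- n = 100 per arm (about 200 randomised 1:1, Protocol 9.5).
- r, the true risk of a multi-system reaction: assumed 1% to 5%.
- c, the share of these recognisable as such from the coded terms: assumed 100%, 50% or 25%.

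Expected number classified = n × r × c. Chance that the arm shows none so classified = (1 − r × c)^n.

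| r | c = 100% | c = 50% | c = 25% |
|---|---|---|---|
| 1% | 1.0; 37% | 0.5; 61% | 0.25; 78% |
| 2% | 2.0; 13% | 1.0; 37% | 0.5; 61% |
| 3% | 3.0; 5% | 1.5; 22% | 0.75; 47% |
| 5% | 5.0; 0.6% | 2.5; 8% | 1.25; 28% |

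For example, at r = 3% and c = 50%: (1 − 0.015)^100 = 0.221.

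**5. Effect on the planned test.** With 100 per arm, Fisher's exact test gives p = 0.029 for 6 versus 0. If half of the six are recognised, 3 versus 0 gives p = 0.246.

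**6. If recognition differed by arm.** With an equal true risk of 5% and recognition of 90% in one arm and 40% in the other, the expected counts are 100 × 0.05 × 0.9 = 4.5 and 100 × 0.05 × 0.4 = 2.0. These fractions are invented to show the mechanism and are not estimates.

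**The case against.** The strongest reply is that the events are not lost. The SAP has a separate identifier for IRRs and compares them by arm, a recorded diagnosis of anaphylaxis should be found by the narrow search, and serious reactions also appear in the SAE summaries. This stands. A reader might infer that multi-system reactions go uncounted, or are undercounted in one arm in particular. The documents support neither: the gap is in classification, and they show no direction or size for any difference between arms.

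Second, the protocol does not bar symptoms from the adverse-event page. Section 8.3.3.1 asks for data in addition, and 10.3.4 applies only where a diagnosis is possible. The ARIA text in 7.1.3, by contrast, says outright that symptoms are not to be reported as adverse events. So some symptom terms may reach the coded data, and a search with no symptom terms at all is the extreme case. This also stands. It reduces the gap without closing it.

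Third, the two-organ-system wording is an example in a donanemab rechallenge rule and, in 8.3.3.1, a sampling trigger paired with severity. A reader might take it as the protocol's definition of anaphylaxis, but it is not one. Using it in analysis is a choice that must be declared.

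Fourth, the CRF is itself opened on the investigator's judgement that a reaction occurred. It can reclassify recognised reactions but cannot find those recorded as something else. Its fields are not in the documents, so whether it supports every element of a rule, such as timing, has to be checked.

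Finally, safety is descriptive here and lies outside the gated tests. At an assumed 3% risk, even fully recognised counts of 3 versus 0 would not be significant. SAP 4.1 also allows exploratory analyses, but a case definition chosen after open-label safety data have been seen carries less weight than one fixed beforehand.

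**Conclusion.** The point holds as a gap in classification. Case finding uses coded TEAEs only, sites are steered towards diagnosis terms on that page, and the form with the signs and symptoms feeds no planned output. Whether a multi-system reaction is shown as possible anaphylaxis therefore depends largely on the term chosen by an investigator who knows the arm.

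The documents cannot settle the size. The illustrations rest on assumed risks and recognition fractions and describe missing classifications, not missing events. They show only that, at about 100 per arm and low risks, a few differently labelled cases could change how the comparison reads. No primary or key secondary conclusion is affected. The change is worth making because it is cheap and concerns a topic of special interest.

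**What to change.** In SAP 4.7.2, keep the SMQ and preferred-term searches and add:

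- The number and percentage of participants, by arm, with a recorded reaction involving two or more organ systems, derived from the hypersensitivity CRF and compared with the Fisher's exact test already planned.
- A prespecified rule that assigns signs and symptoms to organ systems, applied identically in both arms and without reference to arm.
- A listing of the hypersensitivity CRF, as is already planned for the hepatic-safety CRF.
- A statement that this is an analysis category taken from the example wording in Protocol 8.3.3.1 and 8.3.3.2, that it is not a formal definition of anaphylaxis, and that it reclassifies only reactions for which the CRF was completed.

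Cost: SAP wording, one derivation, one table, one listing and some coding of CRF signs and symptoms, after checking that the CRF fields support the rule. No visit, procedure or clinical rule changes.
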